9.2 DOCUMENTATION OF ADVERSE EVENTS

All AEs will be captured from the time the ICF is signed. Any AEs that are ongoing at the Study Termination Visit from Study TDE-PH-310 should be recorded as continuing AEs in this open-label study. An AE or SAE occurring during the study must be documented in the subject's source documents and on the appropriate eCRF page. Information relating to the AE such as onset and cessation date and times, intensity, seriousness, relationship to study drug, and outcome is also to be documented in the eCRF (see Appendix 15.4 for definitions). Where possible, AEs should be recorded using standard medical terminology. If several signs

or symptoms are clearly related to a medically defined diagnosis or syndrome, the diagnosis or syndrome should be recorded on the eCRF page, not the individual signs and symptoms.

All AEs should be followed until either resolution (or return to normal or baseline values), until they are judged by the Investigator to no longer be clinically significant, or for up to 30 days, if the AE extends beyond the final visit. All SAEs that occur during the study will be followed until resolution, death, or the subject is lost to follow-up even if they are ongoing more than 30 days after completion of the final visit. Supplemental measurements and/or evaluations may be necessary to investigate fully the nature and/or causality of an AE or SAE. This may include additional laboratory tests, diagnostic procedures, or consultation with other healthcare professionals. The eCRF pages should be updated with any new or additional information as appropriate.

9.3 REPORTING RESPONSIBILITIES OF THE INVESTIGATOR

All SAEs, regardless of expectedness or causality, must be reported to the Sponsor within 24 hours of awareness by fax (+ 1 [contact] [U.S./Japan] or [name] [Europe/ROW]) or email ([contact]). A completed SAE report form along with any relevant hospital records and autopsy reports should be provided to Global Drug Safety at United Therapeutics Corp. A follow-up SAE report form must be forwarded to Global Drug Safety at United Therapeutics Corp. within 48 hours of the receipt of any new/updated information. The Investigator must also promptly notify their Investigational Review Board (IRB) or Ethics Committee (EC) of the SAE, including any follow-up information, in accordance with applicable national regulations and guidelines set forth by the IRB or EC.

9.4 PREGNANCY

If a study subject becomes pregnant during participation in this clinical study, site staff must notify the Sponsor within 24 hours of learning of the pregnancy by completing the Pregnancy Notification Form and either faxing or emailing this form to Global Drug Safety at United Therapeutics Corp. (+ 1 [contact] [U.S./Japan] or [name] [Europe/ROW]) or [contact]). Subjects who become pregnant during the study will be withdrawn

from active participation in the study and will discontinue study drug after an appropriate period of down-titration.

United Therapeutics Global Drug Safety Department will follow up with the Investigator to ensure appropriate data are provided regarding the outcome of the pregnancy, and to request that the Investigator complete a Pregnancy Outcome Report Form. Pregnancy only becomes an AE/SAE if there is an abnormal outcome, a spontaneous abortion, a termination for medical reasons other than PAH, or a congenital anomaly in the offspring.

9.5 SAFETY REPORTS

In accordance with national regulations, the Sponsor or designee, will notify the regulatory agencies, Investigators, IRBs, and/or ECs of all relevant AEs (usually those that are considered to be possibly attributable to study drug and are both serious and unexpected) in accordance with the applicable national regulations. The Investigator must report these SAEs to their IRB or EC in accordance with applicable national regulations and guidelines set forth by the IRB or EC.

10 STATISTICAL CONSIDERATIONS

10.1 DATA PROCESSING

Subject data will first be documented in the subject's source documents, and then transferred into the eCRF. Site personnel will be responsible for recording all subject's data into the eCRF. Data for any subject who signs an informed consent form will be captured in the eCRF. The eCRF screens are to be reviewed by the Principal Investigator for completeness and accuracy. The Principal Investigator must sign each subject's eCRF to signify their approval of the data. The database will be final when final query resolution has been completed and all data management quality control procedures are complete.

10.2 SAMPLE SIZE

No formal sample size calculation has been conducted. All eligible subjects from TDE-PH-310 may enter this study.

10.3 ANALYSIS PLAN

All safety and efficacy data will be summarized in tables and listings and analyzed for trends over time. No formal hypothesis testing is planned.

The safety population will be defined as all subjects in the study that received UT-15C at any time during the course of the study. Safety analyses will be performed on the safety population. All AEs as recorded by the Investigators will be assigned MedDRA preferred terms by the Sponsor for reporting purposes.

10.4 OTHER ANALYSES

Pharmacogenomic samples will be evaluated for genetic variants. Other exploratory analyses may be conducted based on available study data.

11 PACKAGING AND FORMULATION

11.1 CONTENTS OF STUDY DRUG

United Therapeutics Corp. will supply UT-15C for administration during the study. UT-15C tablets will be provided as 0.125, 0.25, 0.5, 1, and 2.5 mg strengths for the study. The UT-15C tablets are sustained release osmotic tablets. Active treatment will be UT-15C tablets provided as 0.125, 0.25, 0.5, 1, and 2.5 mg strengths for the study. Each tablet contains either 0.125 mg treprostinil (equivalent to 0.15875 mg treprostinil diethanolamine), 0.25 mg treprostinil (equivalent to 0.3175 mg treprostinil diethanolamine), 0.5 mg treprostinil (equivalent to 0.635 mg treprostinil diethanolamine), 1 mg of treprostinil (equivalent to 1.27 mg treprostinil diethanolamine), 2.5 mg of treprostinil (equivalent to 3.17 mg treprostinil diethanolamine). The 0.125, 0.25, 0.5, 1, and 2.5 mg tablets are colored blue, green, white, yellow, and pink, respectively. UT-15C tablets will be provided in child resistant bottles each containing 100 tablets, or in other appropriate packaging configurations as may be required.

11.2 LABELING

Each bottle will be labeled in accordance with applicable national regulations, to include at least the following information: study drug, study reference code, strength, quantity, route of administration, manufacture or expiry date, lot number, Sponsor name, address and telephone number, and storage conditions. The labels on the bottles may include blank fields for sites to

document the following information specific to each bottle, including but not limited to, Investigator name, subject number / initials, and date dispensed.

11.3 STORAGE AND HANDLING OF CLINICAL TRIAL MATERIAL

All study drug will be stored at room temperature (up to 25°C with brief excursions to 30°C permitted). Study drug should not be frozen, refrigerated, or exposed to heat. Site personnel should refer to investigational medicinal product labeling or regulatory submissions for specific requirements by country or region in accordance with local regulations or guidance.

Study drug at the investigational site will be stored in a securely locked cabinet or enclosure with appropriate temperature monitoring. Access should be strictly limited to the Investigators and their designees. Neither the Investigators nor any designees may provide study drug to any person not participating in this study.

The pharmacist or appropriate personnel at the investigational site will deliver and retrieve each bottle assigned to the subject at each study visit during the course of the study. Subjects should be instructed to return all study drug, including empty bottles, to the appropriate study personnel at every protocol-required visit.

11.4 SUPPLY AND RETURN OF CLINICAL TRIAL MATERIAL

Study sites will be supplied with a sufficient quantity of UT-15C to begin enrollment in the study. An IVRS/IWRS will be utilized to manage resupply with respect to each subject's visit schedule. If required, additional study drug may be dispensed to a subject between protocol-required visits. At each protocol required visit, all study drug dispensed to the subject should be returned to the study site (including empty and unopened bottles). A new supply of study drug will be dispensed at each protocol-required visit.

11.5 DRUG ACCOUNTABILITY

The Investigator is responsible for study drug accountability and reconciliation overall and on a per subject basis. Drug accountability records will be maintained during the study and these records will include: the amount of study drug received from the Sponsor, the amount dispensed to each subject, and the amount of unused drug. At each visit, site personnel should assess drug dispensed, drug returned, and dosing information to confirm drug accountability

and compliance. Once a representative from the Sponsor is able to confirm drug accountability for that subject, study drug will be returned to a Sponsor designated location for destruction. Study drug will not be destroyed on-site by the study staff or in the pharmacy.

12 REGULATORY AND ETHICAL OBLIGATION

12.1 ICH GCP OR APPLICABLE REGULATORY REQUIREMENTS

The study will be conducted in accordance with ICH GCP guidelines and all applicable national regulations. The Sponsor will obtain the required approval from each national regulatory authority to conduct the study. During the conduct of the study, an annual development safety update report will be compiled by the Sponsor for submission to those regulatory authorities and IRBs/ECs that require it. Any additional national reporting requirements as specified by the applicable regulations, regulatory authorities, or IRB/EC will also be fulfilled during the conduct of the study.

12.2 INFORMED CONSENT REQUIREMENTS

Before a subject is enrolled in the study, the Investigator or his/her authorized designees must explain the purpose and nature of the study, including potential benefits and risks and all study procedures to the subject. The subject must sign and date an IRB/EC-approved ICF prior to the conduct of any study-related activities. A copy of the signed ICF will be given to the subject and the original will be retained in the study site's records.

12.3 INDEPENDENT ETHICS COMMITTEE/INSTITUTIONAL REVIEW BOARD

Prior to study initiation at each site, the Investigator will obtain approval for the study from an appropriate IRB/EC and provide the Sponsor with a copy of the approval letter. The IRB/EC must also review and approve the study site's informed consent form and any other written information provided to the subject prior to enrollment, as well as any advertising materials used for subject recruitment. Copies of the ICF and advertising materials must be forwarded to the Sponsor for review before submission to the IRB/EC prior to the start of the study.

If, during the study, it is necessary to amend either the protocol or the ICF, the Investigator is responsible for obtaining IRB/EC approval of these amended documents prior to

implementation. Copies of the IRB/EC correspondence and approval letters must be sent to the Sponsor.

During the conduct of the study, an annual progress report will be compiled by the Sponsor for submission to those IRBs/ECs that require it.

A written summary of the study will be provided by the Investigator to the IRB/EC following study completion or termination according to the IRB or EC standard procedures. Additional updates will also be provided in accordance with the IRB/EC's standard procedures.

12.4 PRESTUDY DOCUMENTATION REQUIREMENTS

Before the commencement of the clinical study, the following documents (at minimum) will be provided to the site: Investigator's Brochure, Protocol, ICF, Budget Agreement, and access to an eCRF.

The site will be required to provide the following documents (at minimum) to United Therapeutics Corp. or designee prior to study start: Signature page of the protocol, Form FDA 1572, IRB/EC Composition and Roster, IRB/EC protocol and informed consent approval letters, Curriculum Vitae of study staff listed on the Form FDA 1572, and authorized clinical study agreement (as required).

12.5 SUBJECT CONFIDENTIALITY

Every effort will be made to keep medical information confidential. United Therapeutics Corp., regulatory bodies, and the IRB/EC governing this study may inspect the medical records of any subject involved in this study. The Investigator may release the subject's medical records to employees or agents of the Sponsor, the IRB/EC or appropriate local regulatory agencies for purposes of checking the accuracy of the data. A unique number will be assigned to all subjects and any report published will not identify the subjects by name.

13 ADMINISTRATIVE AND LEGAL OBLIGATIONS

13.1 PROTOCOL AMENDMENTS AND STUDY TERMINATION

Protocol amendments that could potentially adversely affect the safety of participating subjects or that alter the scope of the investigation, the scientific quality of the study, the

experimental design, dosages, duration of therapy, assessment variables, the number of subjects treated, or subject selection criteria may be made only after consultation between United Therapeutics Corp. or its designee and the Investigator.

All protocol amendments must be submitted to and approved by the appropriate regulatory authorities and IRB/EC prior to implementation.

A report documenting study termination must also be submitted to and acknowledged by the appropriate IRB/EC for each study site.

At the end of the study, where applicable, a final report will be provided to the local regulatory agencies.

13.2 STUDY DOCUMENTATION AND STORAGE

In accordance with federal/national regulations, ICH GCP guidelines, the Investigator must retain study records for at least 2 years after the last approval of a marketing application in an ICH region and until there are no pending or contemplated marketing applications in an ICH region or at least 2 years have elapsed since the formal discontinuation of clinical development of the investigational product. For Investigators in the European Economic Area, the study records should be maintained for at least 15 years after study discontinuation. The Investigator must notify United Therapeutics Corp. before any disposal or change in location of study records.

13.3 STUDY MONITORING AND DATA COLLECTION

In accordance with federal/national regulations, ICH GCP guidelines, monitors for United Therapeutics Corp. or its designee will periodically contact the site and conduct on-site visits. During these visits, the monitor will at a minimum: confirm ethical treatment of subjects, assess study progress, review data collected, conduct source document verification, verify drug accountability periodically, and identify any issues requiring resolution.

The Investigator must agree to allow the monitor direct access to all relevant documents and to allocate his/her time and his/her staff to the monitor to discuss any findings or any relevant issues. In addition, auditors for United Therapeutics Corp. or its designee may periodically contact the site and conduct on-site visits.

15 APPENDICES**15.1 PROCEDURE FOR SIX MINUTE WALK EXERCISE TEST AND BORG
DYSPNEA SCORE**General Procedures

The 6-Minute Walk exercise test should be administered by the same tester and on the same course at each study site throughout the study for a given subject. The administration of the test and specifications of the testing area should be generally consistent with the American Thoracic Society guidelines and the usual practice of the investigative site [ATS guidelines; 2002].

The area used for the 6-Minute Walk Test should be pre-measured at approximately 30 meters in length (but no shorter than 15 meters [16 yards or 50 feet] in length at minimum) and at least 2 to 3 meters in width. There should be no turns or curves to the 6-Minute Walk area. The length should be marked with gradations at least every 3 meters to ensure the accurate measurement of the distance walked. The area should be well ventilated. The tester may be at the starting end of the corridor or at the midpoint of the corridor with a stop-watch. Intermittent rest periods are allowed if the subject can no longer continue. If the subject needs to rest briefly, he/she may stand or sit and then begin again when he/she is sufficiently rested but the clock will continue to run. At the end of 6 minutes, the tester will call “stop” while simultaneously stopping the watch and then measure the distance walked. The Borg dyspnea rating will be administered immediately following completion of the 6MWT.

Instructions to the Subject

Subjects will be instructed that the preceding meal should be light. Subjects should be told to wear comfortable clothing and sneakers or comfortable walking shoes. The person administering the test will use the following exact dialogue with the subject:

“The purpose of this test is to find out how far you can walk in 6 minutes. You will start from this point and follow the hallway to the marker (eg, chair) at the end, turn around and walk back. When you arrive back at the starting point you will go back and forth again. You will go back and forth as many times as you can in the 6-minute period. You may stop and rest if you need to. Just remain where you are until you can go on again. However, the most important thing about the test is that you cover as much ground as you

possibly can during the 6 minutes. I will tell you the time, and I will let you know when the 6 minutes are up. When I say STOP, please stand right where you are.”

After these instructions are given to the subject, the person administering the test will then ask:

“Do you have any questions about the test?”

“Please explain to me what you are going to do.”

The person administering the test will then start the test by saying the following to the subject:

“Are you ready?”

“Start when I say ‘GO.’”

The person administering the test will tell the subject the time at 2 and 4 minutes by saying:

“You have completed 2 minutes.”

And then by saying:

“You have completed 4 minutes.”

No other instruction or encouragement will be given during the test. Eye contact with the subject should be avoided during the test.

Following the walk, the person administering the test will obtain a rating of dyspnea using the Borg Scale. The person will use the following dialogue:

“I would like to use the following scale to indicate the maximal shortness of breath you had during the walk test (indicate the Borg Scale). If there was no shortness of breath at all you would point to 0; if the shortness of breath was not very great you would choose from 0.5 to 2; if you were somewhat more short of breath you would select 3; and if the breathing was getting very difficult, you would choose 4 to 9, depending on just how hard it was; 10 represents the greatest shortness of breath you have ever experienced in your life, and if you feel more short of breath than you have ever been in your life before, choose a number greater than 10 that represents how short of breath you feel. If one of the numbers does not exactly represent how short of breath you are, then you can choose a fraction between. For example, if you had shortness of breath somewhere between 4 and 5, you could choose 4 ½.

15.2 WHO FUNCTIONAL CLASS FOR PAH

Class I: Patients with pulmonary hypertension but without resulting limitation of physical activity. Ordinary physical activity does not cause undue dyspnea or fatigue, chest pain, or near syncope.

Class II: Patients with pulmonary hypertension resulting in slight limitation of physical activity. These subjects are comfortable at rest, but ordinary physical activity causes undue dyspnea or fatigue, chest pain or near syncope.

Class III: Patients with pulmonary hypertension resulting in marked limitation of physical activity. They are comfortable at rest. Ordinary activity causes undue dyspnea or fatigue, chest pain, or near syncope.

Class IV: Patients with pulmonary hypertension with inability to carry out any physical activity without symptoms. These subjects manifest signs of right heart failure. Dyspnea and/or fatigue may be present even at rest. Discomfort is increased by any physical activity.

15.3 CLINICAL LABORATORY PARAMETERS

Blood Chemistries	Hematology	Other
Sodium	Red Blood Cell Count	NT-proBNP (plasma)*
Potassium	Hemoglobin	Urine dipstick analysis**
Chloride	Hematocrit	Urine pregnancy test***
Bicarbonate/CO ₂	Platelet Count	
Albumin	White Blood Cell Count (no differential)	
Blood Urea Nitrogen/Urea		
Total Bilirubin		
Indirect Bilirubin		
Direct Bilirubin		
Alkaline Phosphatase		
Alanine Aminotransferase (ALT)		
Aspartate Aminotransferase (AST)		
Gamma-glutamyl transferase (GGT)		
Creatinine		

Visit Test Schedule

Visit	Labs Collected
Baseline/Study Entry****	Chemistries, Hematology, NT-proBNP, urine dipstick, urine pregnancy***
Week 6 Visit	Urine pregnancy***
Week 12 Visit	Chemistries, Hematology, urine pregnancy***
Follow-up Visits*****	Chemistries, Hematology, NT-proBNP*, urine pregnancy***
Study Termination Visit	Chemistries, Hematology, urine dipstick, urine pregnancy***

* NT-proBNP collected at Baseline/Study Entry and Follow-up Visit (Week 48) only

** pH, specific gravity, presence of protein or blood

*** For women of childbearing potential (WOCBP)

**** Baseline/Study Entry clinical laboratory assessments for this study are those collected at the last visit (Study Termination) from study TDE-PH-310 and prior to initiation of open-label UT-15C.

***** During Follow-up Visits, clinical laboratory samples should be collected at the first Follow-up Visit and every other Follow-up Visit thereafter.

15.4 GUIDELINES AND DEFINITIONS FOR RECORDING ADVERSE EVENTS

The Principal Investigator or a designated member of his/her staff will probe each subject for any AEs that may have occurred. The Investigator should always ask the same question when conducting the verbal probe in order to ensure uniformity between subjects. The Investigator should ask:

“How are you doing (feeling)?”

Based on the subject’s response to this question, the Investigator should ask additional questions relevant to the specific complaint such as:

“How severe is/was the symptom?”

“How often did the symptom occur?”

“How long did the symptom last?”

Using provided definitions, the Investigator will then:

(1) rate the intensity and seriousness of the AE, (2) estimate the causality of the AE to study drug, and (3) note actions taken to counteract the AE.

Definitions of Intensity, Seriousness, Causality, Action Taken, and OutcomeINTENSITY

An assessment of the relative intensity (severity) of an AE is based on the Investigator’s clinical judgment. The maximum intensity encountered during the evaluation period should be checked. The assessment of intensity should be independent of the assessment of the seriousness of the AE.

SERIOUSNESS

A SAE is one that represents an actual or potential significant hazard. This includes, but is not limited to, an event that is fatal, life-threatening, permanently or severely disabling, requires or prolongs inpatient hospitalization, is a congenital abnormality (offspring of subject) or is medically significant (important medical events that may not result in death, be life-threatening, or require hospitalization may be considered a SAE when, based upon

appropriate medical judgment, they may jeopardize the subject and may require medical or surgical intervention to prevent one of the outcomes listed in this definition).

CAUSALITY

An estimate of causality between a specified AE and the study drug is made by the Investigator. Definitions of the categories follow:

- NOT RELATED - there is not a temporal relationship to study drug administration (too early, or late, or study drug not taken), or there is a reasonable causal relationship between another drug, or concurrent disease and the SAE
- POSSIBLE - there is a reasonable causal relationship between the study drug and the SAE. Dechallenge information is lacking or unclear
- PROBABLE - there is a reasonable causal relationship between the study drug and the SAE. The event responds to dechallenge. Rechallenge is not required

ACTION TAKEN

- TEST AGENT DOSE MODIFICATION*
- Dose Increased - the dose or regimen of the test agent was increased
- Dose Not Changed - the dose or regimen of the test agent was not changed
- Dose Reduced - the dose or regimen of the test agent was decreased
- Drug Interrupted - administration of the test agent was stopped temporarily
- Drug Withdrawn - administration of the test agent was stopped permanently and not restarted
- Unknown - changes to the administration of the test agent cannot be determined

*NOTE: Only the last test agent action should be recorded in the eCRF.

OUTCOME

- Fatal – The study subject died
- Not Recovered / Not Resolved – The AE was ongoing
- Recovered / Resolved – The AE resolved
- Recovered / Resolved with Sequelae – The AE is considered resolved however there is a residual sequelae
- Recovering / Resolving – The AE is improving but is not yet completely recovered / resolved
- Unknown – The outcome of the AE cannot be determined

15.5 EXPECTED EVENTS ATTRIBUTABLE TO THE PROGRESSION OF PULMONARY ARTERIAL HYPERTENSION (SYSTEM ORGAN CLASS AND PREFERRED TERM, VER. 16.0)

Abdominal pain (Gastrointestinal disorders; ABDOMINAL PAIN)	Hemoptysis (Respiratory, thoracic & mediastinal disorders; HAEMOPTYSIS)
Anorexia (Metabolism and nutrition disorders; ANOREXIA)	Hypoxia (Respiratory, thoracic & mediastinal disorders; HYPOXIA)
Ascites (Gastrointestinal disorders; ASCITES)	Loss of consciousness (Nervous system disorders; LOSS OF CONSCIOUSNESS)
Cardiac arrhythmia (Cardiac disorders; ARRHYTHMIA)	Nausea (Gastrointestinal disorders; NAUSEA)
Cardiac arrest (Cardiac disorders; CARDIAC ARREST)	Edema (General disorders and administration site conditions; OEDEMA)
Heart failure (including exacerbation of) (Cardiac disorders; CARDIAC FAILURE)	Orthopnea (Cardiac disorders; ORTHOPNOEA)
Chest pain (General disorders and administration site conditions; CHEST PAIN)	Pallor (Vascular disorders; PALLOR)
Cardiovascular collapse (Vascular disorders; CIRCULATORY COLLAPSE)	Palpitations (Cardiac disorders; PALPITATIONS)
Cor pulmonale (Cardiac disorders; COR PULMONALE)	Cool extremities (General disorders and administration site conditions; PERIPHERAL COLDNESS)
Cough (Respiratory, thoracic & mediastinal disorders; COUGH)	Pulmonary arterial hypertension, exacerbation of (Vascular disorders; PULMONARY ARTERIAL HYPERTENSION)
Cyanosis (Cardiac disorders; CYANOSIS)	Sudden death (Cardiac disorders; SUDDEN DEATH)
Dizziness (Cardiac disorders; DIZZINESS)	Syncope (Cardiac disorders; SYNCOPE)
Dyspnea at rest (Respiratory, thoracic & mediastinal disorders; DYSPNOEA)	Vasovagal reaction (Nervous system disorders; SYNCOPE VASOVAGAL)
Dyspnea on exertion (Respiratory, thoracic & mediastinal disorders; DYSPNOEA EXERTIONAL)	Tachycardia (Cardiac disorders; TACHYCARDIA)
Paroxysmal nocturnal dyspnea (Cardiac disorders; DYSPNOEA PAROXYSMAL NOCTURNAL)	Vomiting (Gastrointestinal disorders; VOMITING)
Exercise intolerance (General disorders and administration site conditions; EXERCISE TOLERANCE DECREASED)	Weight loss (Investigations; WEIGHT DECREASED)
Fatigue (General disorders and administration site conditions; FATIGUE)	Weight gain (Investigations; WEIGHT INCREASED)

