4.2 EXCLUSION CRITERIA

A subject is not eligible to participate in this study if any of the following criteria apply:

1. The subject is pregnant or lactating.
2. The subject has received infused or inhaled prostacyclin therapy for 29 days or more.
3. The subject was prematurely discontinued from Study TDE-PH-310 for reasons other than a clinical worsening event.
4. The subject developed a concurrent illness or condition during the conduct of TDE-PH-310 which, in the opinion of the Investigator, would represent a risk to overall health if they enrolled in this study.

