4.3 PRESCRIBED THERAPY

4.3.1 Concomitant Medications

In this open-label study, there are no restrictions on concomitant medications, including the approved PAH therapies, with the exception of the permanent addition (29 days or more) of prostacyclin or prostacyclin analogue therapy. Subjects who receive permanent prostacyclin or prostacyclin analogue therapy must discontinue this open-label study.

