9.3.3 PAH History

The listing of PAH history will be organized by treatment group in the parent study, and will include the subject number, the date of initial PAH diagnosis, number of years since PAH diagnosis, etiology, WHO Functional Class at Baseline, 6MWD at Baseline, Borg dyspnea score at Baseline, background PAH therapy (endothelin receptor antagonist [ERA] alone, phosphodiesterase type 5 inhibitor [PDE-5I] alone, or soluble guanylate cyclase [sGC] stimulator alone), and background PAH medication name. The number of years since PAH diagnosis will be calculated based on the first UT-15C dose date in the TDE-PH-311 study. The summary of PAH history will include descriptive statistics for years since PAH diagnosis and categorical summaries for etiology and background PAH therapy at randomization in the parent study.

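### The causality definitions in Protocol 15.4 let one adverse event be both NOT RELATED and POSSIBLE or PROBABLE, with no tie-break, so plausibly drug-related events can drop out of the related-event tables

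*Protocol*

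**What the plan says.** Protocol 15.4 introduces the causality scale for adverse events in general: "An estimate of causality between a specified AE and the study drug is made by the Investigator". Protocol 9.2 applies it to every recorded event, since "relationship to study drug, and outcome is also to be documented in the eCRF", and refers back to 15.4 for the definitions. Section 15.4 tells the Investigator to rate from the definitions it supplies.

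The three definitions are:

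- NOT RELATED has two alternatives. Either the timing rules study drug out, "or there is a reasonable causal relationship between another drug, or concurrent disease and the SAE". Meeting one of the two is enough for this rating.
- The middle category turns on study drug being a plausible cause while withdrawal of the drug tells us little. It reads "POSSIBLE - there is a reasonable causal relationship between the study drug and the SAE. Dechallenge information is lacking or unclear". Nothing in it asks whether some other cause is present.
- The top category shares the study-drug criterion of the middle one, and differs in asking for a positive response when the drug is withdrawn. It too is silent on other causes.

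All three say SAE, although the scale is meant for all adverse events.

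SAP 11.1 counts as related those events rated probably or possibly related to UT-15C. The rating feeds Table 14.3.1.5 (related serious events), Table 14.3.1.6 (related events), and two of the six lines of the overall summary, Table 14.3.1.1 (subjects with any study-drug-related event, and with any study-drug-related severe event).

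**The concern.** A causality scale should put each event in exactly one category. Here the presence of another explanation is enough for NOT RELATED, while POSSIBLE and PROBABLE do not require other explanations to be absent. When both kinds of cause are reasonable, two ratings are correct under the text and the choice is left to the site.

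The choice works in one direction. POSSIBLE or PROBABLE keeps the event in the related-event tables; NOT RELATED removes it. Relative to a rule that counts every event with a reasonable study-drug cause, overlap cases can only lower the related counts. Sites that resolve the overlap differently will also not be counting the same thing.

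This bears on a stated aim. Long-term safety is a secondary objective (Protocol 2.2), all subjects receive UT-15C (5.1) and there is no control group (synopsis). With no untreated comparator, the related-event tables rest wholly on the Investigator's rating.

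**Working it through.** The plan gives no figure to reproduce. The check is whether the three definitions, applied literally, give one rating per event, and whether any other text settles the cases where they do not.

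**Step 1: enumerate the cases.** Four facts enter the definitions: timing plausible (yes or no), study drug a reasonable cause (yes or no), another drug or concurrent disease a reasonable cause (yes or no), and dechallenge (responds; lacking or unclear; no response). That is 2 × 2 × 2 × 3 = 24 combinations. I assume that study drug cannot be a reasonable cause when the timing is implausible, which removes 2 × 3 = 6 and leaves 18.

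| Timing plausible | Study drug reasonable | Other drug or disease reasonable | Dechallenge | Rating under 15.4 | Cases |
|---|---|---|---|---|---|
| yes | yes | yes | responds | NOT RELATED and PROBABLE | 1 |
| yes | yes | yes | lacking or unclear | NOT RELATED and POSSIBLE | 1 |
| yes | yes | yes | no response | NOT RELATED | 1 |
| yes | yes | no | responds | PROBABLE | 1 |
| yes | yes | no | lacking or unclear | POSSIBLE | 1 |
| yes | yes | no | no response | none | 1 |
| yes | no | yes | any | NOT RELATED | 3 |
| yes | no | no | any | none | 3 |
| no | no | either | any | NOT RELATED | 6 |

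One rating: 1 + 1 + 1 + 3 + 6 = 12. Two ratings: 2. No rating: 1 + 3 = 4. Total: 12 + 2 + 4 = 18. These are counts of logical cases, not frequencies of events.

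**Step 2: look for a tie-break.** Protocol 9.2 only points back to 15.4. Sections 3.3.2.4 and 9.1.3 decide whether a PAH-type event is recorded as an adverse event, not how it is rated. Sections 9.3 and 9.5 concern reporting. SAP 11.1 uses the ratings as recorded. None gives an order of precedence.

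**Step 3: can the overlap arise?** The other-drug alternative is enough. Under Protocol 4.3.1, "there are no restrictions on concomitant medications, including the approved PAH therapies", apart from permanent prostacyclin therapy. SAP 9.3.3 summarises "background PAH therapy at randomization in the parent study", and SAP 9.3.4 summarises both medications continued from the parent study and those added in this one. Subjects are thus expected to be taking other drugs alongside UT-15C.

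**Step 4: count the outputs that depend on the rating.** The adverse event summary tables are 14.3.1.1 to 14.3.1.7 and 14.3.1.9, which is 8. Tables 14.3.1.5 and 14.3.1.6 depend on the rating in full, and 14.3.1.1 in 2 of its 6 lines: 3 of 8. The other 5 (14.3.1.2, 14.3.1.3, 14.3.1.4, 14.3.1.7 and 14.3.1.9) do not.

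**A minor mismatch nearby.** Protocol 3.3.2.4 records a PAH symptom as an adverse event if it is new. Section 9.1.3 has no such criterion.

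**The case against.** The strongest case on the other side has four parts.

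*An Investigator who thinks study drug a reasonable cause would not choose NOT RELATED.* For a listed PAH-progression event that is non-serious and of expected severity, 9.1.3 requires entry as an adverse event only because drug causation is reasonably possible, so NOT RELATED would contradict the reason for entry. That is a fair argument against the choice, but it is an inference that the protocol does not state as a rating rule. It also covers only that one route of entry and only the events on the Appendix 15.5 list.

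*No concrete instance is shown for the other-drug alternative.* This stands in part. The documents name no co-medication effect that coincides with a UT-15C effect, and SAP 9.3.3 describes background therapy at parent-study randomization rather than at the time of an event. It limits what can be said about frequency; it does not remove the overlap in the definitions.

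*The listings show the rating event by event.* True, but the fields in SAP 11.1 include no alternative cause, so a NOT RELATED rating given in an overlap case cannot be told apart from any other.

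*The study is uncontrolled, with no hypothesis test (Protocol 10.3).* This stands. No inferential result is at risk; the effect is on a descriptive safety result.

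Using SAE where AE is meant is editorial, since 15.4 itself speaks of the causality of the AE.

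**Conclusion.** The point holds. The definitions of NOT RELATED and of POSSIBLE or PROBABLE overlap whenever study drug and another drug or a concurrent disease are both reasonable causes and dechallenge is not negative. Nothing in either document resolves it. The consequence is confined to 3 of the 8 adverse event summary tables. It is worth correcting because the rule itself, followed as written, permits the misclassification, and rewording is cheap.

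The conclusion rests on a literal reading of 15.4 and on the timing assumption stated in the working. How many events are affected cannot be estimated.

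Three stronger readings are not supported:

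- A reader might infer that every PAH-type event is caught because every subject has PAH. The documents do not say that PAH is a concurrent disease. In Protocol 4.2 similar wording describes something that arose later: "The subject developed a concurrent illness or condition during the conduct of TDE-PH-310".
- A reader might infer that safety reporting is compromised. Protocol 9.3 requires all serious events to go to the Sponsor whatever their causality. Onward notification under 9.5 usually turns on attribution to study drug, but 9.5 does not say that the 15.4 rating decides, so an effect there is possible but not shown.
- A reader might try to size the problem from terms, such as nausea, that are both prostacyclin effects and listed progression events. That counts terms, not events, and the protocol's lists of prostacyclin effects are not presented as complete.

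**What to change.** In Protocol 15.4:

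1. Define NOT RELATED as applying only when there is no reasonable possibility that study drug contributed.
2. Assign events with a reasonable study-drug cause that do not respond to dechallenge. For example, let POSSIBLE mean a reasonable relationship with dechallenge not positive. Step 1 alone would remove the overlap but leave these events without a category.
3. Replace SAE with AE in the three definitions (editorial).

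Applied to the same 18 combinations, steps 1 and 2 give one rating each: 2 PROBABLE, 4 POSSIBLE and 12 NOT RELATED.

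In the data and the SAP, flag ratings made before the change so that Tables 14.3.1.1, 14.3.1.5 and 14.3.1.6 can be read with that in view.

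As a minor matter, reconcile 3.3.2.4 and 9.1.3 on whether a new PAH symptom is recorded as an adverse event.

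The cost is a wording change and a flag, with no new assessment or table. The downsides are somewhat more events counted as possibly related, and a mixture of old and new ratings in the three tables.
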